2. STUDY DESIGN

This study will use a double blind, stratified randomization trial approach involving 36 T2D-HF patients taking standard HF therapies, who will be allocated to either ertugliflozin or placebo in a 1:1 ratio (Table 1 – inclusion and exclusion criteria). For feasibility, participants will be recruited from the >4000 HF patients followed at UHN-MSH heart failure clinics and from heart failure clinics in Groningen, the Netherlands, of whom >40% have T2D. The study will consist of a screening visit, a 4-week run-in phase for those subjects not on stable ACEi/ARB treatment, followed by a 12-week double blind treatment period.

The target population will be invited for screening. Subjects who meet all entry criteria and who are already on a stable dose (no changes in dose or type of drug) of ACEis or ARBs for at least 4 weeks proceed directly to randomization. Subjects who had their ACEi or ARB medication changed during the preceding 4 weeks of the screening visit proceed to a run-in phase during which the type and dose of these drugs are stabilized. Subjects will be randomly assigned to one of the two treatments. Subjects will have their study visit in the morning in fasted condition.

Subjects will be instructed to take the study medication once daily, in the morning, except on study days; on those days, the study drug will be taken after the patient visit.

Measurements:

- During the double blind treatment period, patients will collect a 24-hour urine collection at each visit for measurement of 24-hour protein, albumin, glucose, sodium, potassium, creatinine, and urea excretion. Twenty-four hour urine collections will be performed at: Visits 3, 4 and 8. Routine biochemistry and safety labs will be drawn at screening, during each physiological assessment and at each the specified office safety visits (see visit schedule table below).
- Office systolic and diastolic blood pressure measurements, heart rate, weight, and waist circumference will be performed at screening and at each subsequent physiological testing day and at each office visit (see visit schedule table below).
- Blood will be drawn for measurement of renal function tests, HbA1c, glucose, complete blood count, plasma albumin, RAAS biomarkers, natriuretic peptides, and neurohormones on visits 3, 4 and 8.
- Blood and urine samples will be stored for future exploratory biomarker analyses to study the effect of ertugliflozin in this study population.

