The randomization visit procedures should be completed on a single day under a euglycemic clamp. As part of the study procedures, blood glucose will therefore be maintained between 4-6 mmol/L during the long study days. From a patient perspective, the procedures involved in the trial involve three intravenous needles (for renal function assessments, infusion of insulin and dextrose and finally for blood-letting). The randomization visit procedures will include measures of natriuresis, renal and systemic hemodynamic function, neurohormonal assessments, echocardiography, arterial stiffness, plasma volume, bioimpedence spectroscopy, vital signs, weight and waist circumference, blood and urine samples collection. Cardiac output and systemic vascular resistance will also be measured using non-invasive cardiac monitoring (NICOM). This Version number: 6.0

non-invasive technique is a form of bioelectrical impedance ("bioreatance") to measure thoracic fluid content with electrocardiogram electrode stickers. Beat-to-beat changes in fluid content can be used to derive cardiac output. Then, using measured mean arterial pressure, systemic vascular resistance can be calculated. This entire measurement process takes approximately 15 minutes^{8a}. The first dose of blinded study medication should only be administered one day after all randomization visit procedures have been completed.

Visit 4, 5 and 6

One week after initiation of ertugliflozin/placebo, subjects will return to the renal physiology laboratory for the 1-week assessment (Visit 4), with repeated measures of all physiological parameters described for Visit 3. They will then continue the same treatment allocation for the rest of the trial. A safety visit (vital signs, weight, waist circumference, and physical exam and safety laboratory tests) will be conducted approximately 7-10 days later (Visit 5), and again 4-5 weeks later (Visit 6).

Additional telephone visits will be scheduled as required to follow weight and home blood pressure, in line with usual clinical care. If the patient does not tolerate medication a visit to the out-patient clinic will be scheduled. At the end of the treatment period (at visits 3, 4, and 8), the patient will take study medication *BEFORE* physiological procedures are performed.

Visit 7 and 8

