2.1 Sample size calculation

Sample size: The sample size is based on the primary endpoint of proximal fractional sodium excretion (FE_{Na}), which will be measured using fractional excretion of lithium as a surrogate for proximal sodium handling. Based on preclinical studies, and assuming a baseline FE_{Na} of 22±7, to be able to detect a 40% increase in FE_{Na} with an 80% power and a two-tailed alpha = 0.05, 18 patients per group are required, for a total sample size of n=36. This sample size is similar to those successfully used in previous studies², and sufficient to measure secondary endpoints related to Na⁺ handling^{27,28}, renal function², arterial stiffness, plasma volume⁷, systemic vascular resistance ²⁹ and measures of neurohormonal function^{10,17,18}. Randomization will be stratified to assure equal numbers of HFrEF and HFpEF patients in the ertugliflozin and placebo-treated groups. We anticipate an approximate 50%/50% split in the proportion of participants with HFrEF vs. HFpEF, which will be assessed based on the 2D echo at the time of the baseline physiological testing.

Data Analysis: **The primary outcome** is the difference in proximal sodium reabsorption FE_{Na} (measured using FE_{Li}) with ertugliflozin vs. placebo. **Secondary outcomes** will consist of *within* and *between group* changes in hemodynamic and tubular function parameters and vasoactive mediators in response to combination vs. monotherapy regimens. *Within group* comparisons will be analyzed using repeated measures ANOVA. As in previous work, *between group* comparisons will also be made using a 2-way ANOVA with treatment allocation as the dependent variable. *Post-hoc* analyses will be used to compare means, corrected for multiple comparisons. In pre-specified, exploratory sensitivity analyses, the same endpoints will be examined only in those patients who did not have changes in RAAS inhibitors and/or diuretic agents during the treatment period.

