6.3 Study procedures

Physical examination

Patients will be subjected to physical examination by the principal investigator before inclusion. This physical examination entails a routine investigation of heart, lungs and abdomen. At each visit patients will be asked for adverse events related to urinary tract infections or genital infections.

• 24hr urine collection

Patients are asked to collect 24hr urine at start and end of each treatment period to monitor albuminuria. In total, three 24hr urines are collected during the course of this study. 24hr urine collection instructions will be provided to each patient. The volume of the urine containers is determined when the patient delivers the urine at each visit. Subsequently part of the urine is used for clinical chemistry measurement and the other part stored per instructions in the laboratory manual.

Renal hemodynamic function

GFR and plasma flow measurements will be performed during each of the three physiological assessment visits.

The central laboratory at the UHN will be providing detailed instructions for the renal function tests in a separate laboratory manual. The inulin/PAH will be bought by the investigational site and should be used in accordance with the approved product label and manual instructions. In the event that inulin is not available, then iohexol will be used instead according to label and laboratory manual instructions.

Subject preparation:

After a 10-hr fast, two intravenous (IV) catheters, one in each arm, will be placed in the subject's antecubital vein. One line will be used for the injection of renal function marker solutions. The second line will be used for intermittent blood sampling. On each long study day (Visits 3, 4 and 8), study medication will be taken between after arrival in the laboratory **BEFORE** physiological measurements are obtained.

Blood pressure measurements

Blood pressure will be measured by office blood pressure machine during the outpatient visits. Patients will be in a semi-supine position during the blood pressure measurement. The average of three readings will be used.

Venipuncture

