At each of the visits, approximately 20 ml will be taken for routine blood tests (approximately 20 ml/ 7 visits = 140 ml). At each of the 3 visits to assess kidney function, approximately 24 ml will be taken (total 72 ml), plus another 20 ml at each kidney function visit for measurement of hormones and other factors associated with kidney disease (approximately 20 ml for each of the 3 kidney visits = 60 ml). At the end of each of the 2 treatment periods (Visits 4 and 8), 9 blood samples of 1ml will be taken for ertugliflozin PK analysis (total 18ml). A total of approximately 290 ml of blood will be collected over 12 week period. Additional blood sampling will be take for plasma volume and lithium/sodium excretion measurements as described in the ICF.

- Laboratory measurements All routine laboratory measurements of this study will be assessed at the local laboratories of participating centres.
- Ertugliflozin plasma/urine concentration measurement At the end of the treatment period, during the GFR assessment, a 6 ml blood sample will be drawn for ertugliflozin and its metabolite ertugliflozin-3O-glucuronide measurement.

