ERtugliflozin triAl in DIabetes with preserved or reduced ejeCtion FrAcTion mEchanistic evaluation in Heart Failure: "ERADICATE-HF"

Clinicaltrialgov: NCT03416270

Principal investigator(s):

[name] Division of Nephrology University Health Network, University of Toronto Toronto [contact] E-mail: [contact]

[name] Department of Clinical Pharmacology University Medical Center Groningen Groningen [contact] E-mail: [contact]

Sponsor: University Health Network Toronto, Ontario, Canada

Subsidising party: Merck (investigator initiated study)

Objectives

1. Primary objective:

The primary objective is to determine if acute and chronic ertugliflozin use causes a persistent proximal renal tubular natriuretic effect compared to placebo. Acute means changes from baseline to Visit 4 (1 week), and chronic means changes from baseline to Visit 8 (12 weeks).

2. Secondary objectives:

- 2.1. We will assess whether the proximal renal tubular natriuretic effect of ertugliflozin leads to volume contraction compared to placebo. To this end, we will determine the association between acute and chronic changes to fractional sodium handling and acute and chronic changes in volume.
- 2.2. We will assess whether volume contraction with ertugliflozin leads to a decline in hormones that are activated in heart failure (HF) patients, without activating the sympathetic nervous system (SNS) compared to placebo. To this end, we will determine the association between acute and chronic changes to volume and acute and chronic changes in hormone levels.
- 2.3. We will determine the impact of ertugliflozin on renal function. Specifically, the acute and chronic change in markers of renal hemodynamic function will be measured and compared between ertugliflozin and placebo.
- 2.4. We will determine if ertugliflozin causes a blood pressure lowering effect. Specifically, we will evaluate the acute and chronic change in cardiovascular hemodynamic assessments with ertugliflozin compared to placebo.
- 2.5. We will assess the acute and chronic changes to SNS activation with ertugliflozin use compared to placebo.
- 2.6. We will assess the acute and chronic effects of ertugliflozin on the level of urinary natriuretic modulators normalized to creatinine compared to placebo.
- 2.7. We will characterize the safety of ertugliflozin use compared to placebo.

3. Exploratory objectives:

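### Protocol instructions on when study drug is taken contradict each other at Visits 3, 4 and 8, the three visits that supply the primary FE(Li) data

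*Protocol*

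**What the plan says.** Four protocol statements govern study-drug intake on the physiological study days.

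- Section 2, general instruction: the drug is taken each morning, "except on study days; on those days, the study drug will be taken after the patient visit".
- Section 2, under Visit 3 (Randomization): "The first dose of blinded study medication should only be administered one day after all randomization visit procedures have been completed".
- Section 2, under Visit 4, 5 and 6: "At the end of the treatment period (at visits 3, 4, and 8), the patient will take study medication *BEFORE* physiological procedures are performed".
- Section 6.3, Subject preparation: "On each long study day (Visits 3, 4 and 8), study medication will be taken between after arrival in the laboratory". The sentence goes on to place this intake ahead of the physiological measurements.

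The SAP builds the primary analysis on these visits: "Acute means changes from baseline to Visit 4 (1 week), and chronic means changes from baseline to Visit 8 (12 weeks". Analysis 1.1 fits one mixed model to Visits 3 and 4 and another to Visits 3 and 8. Each contains visit and treatment-by-visit but no treatment main effect, which the SAP justifies by randomisation. Each therefore has one common mean for both arms at Visit 3. The section on general model assumptions adds a participant random intercept, REML and a missing-at-random framework.

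**The concern.** At Visits 4 and 8 a site has two current instructions that exclude each other, and no passage says which governs. Timing decides what the primary estimates mean. It also decides what the pharmacokinetic samples mean, since section 6.3 says that on completion "of each of the 2 treatment periods (Visits 4 and 8), 9 blood samples of 1ml will be taken for ertugliflozin PK analysis". With one centre in Canada and one in the Netherlands, practice could differ by site.

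At Visit 3 the stake is different. Randomisation justifies a common Visit 3 mean only for values obtained before any study drug, and the SAP does not state that condition. If ertugliflozin patients were measured after a dose, part of the treatment effect could already be in the baseline, and the model would read it as chance imbalance.

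**Working it through.** **The text, visit by visit**

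| Visit | Section 2, general | Section 2, Visit 3 rule | Section 2, Visit 4, 5 and 6 | Section 6.3 |
|---|---|---|---|---|
| 3 | after the visit, if read literally | no dose until a day after all procedures | before procedures | before measurements |
| 4 and 8 | after the visit | not applicable | before procedures | before measurements |

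No row is consistent.

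**Visits 4 and 8.** Write E1 for the effect about a day after a dose and E2 for the effect shortly after one. If a share p of patients is measured at the first timing, the estimate targets p × E1 + (1 − p) × E2. The documents give no pre-dose versus post-dose difference in FE(Li) or FE(Na), so E1 − E2 cannot be computed. The timing rule is the same in both blinded arms, so it favours neither.

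**Visit 3.** The plan has no figure of its own here, so this is an illustration.

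Inputs:
- Effect: 40% of a baseline of 22 (section 2.1, Sample size calculation), 0.40 × 22 = 8.8.
- f, the share of that effect already present at Visit 3: assumed.
- rho, the correlation between Visit 3 and follow-up: assumed.

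With a common Visit 3 mean, a random intercept and equal variances, the model's estimate is approximately

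(arm difference at follow-up) − rho × (arm difference at Visit 3).

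If all ertugliflozin patients are dosed first, the expected value is 8.8 − rho × f × 8.8 = 8.8 × (1 − rho × f).

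| rho | f = 0 | f = 0.25 | f = 0.5 |
|---|---|---|---|
| 0.3 | 8.8 | 8.8 × 0.925 = 8.1 | 8.8 × 0.85 = 7.5 |
| 0.5 | 8.8 | 8.8 × 0.875 = 7.7 | 8.8 × 0.75 = 6.6 |
| 0.7 | 8.8 | 8.8 × 0.825 = 7.3 | 8.8 × 0.65 = 5.7 |

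Simulating the SAP 1.1 model (18 per arm, SD 7 from section 2.1, REML) supports the approximation. With f = 0 the mean estimate is 8.7 to 8.8. With f = 0.5 it is 7.3 to 7.5, 6.4 to 6.5 and 5.6 to 5.7 for rho 0.3, 0.5 and 0.7. If only 9 of 18 per arm are dosed first, f = 0.5 gives 8.1, 7.8 and 7.3.

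**Setting post-dose baselines aside.** The simulated mean estimate then returns to 8.7 to 8.9, but the test needs care. With no true effect, a Wald z test at a nominal 5% rejects in 6.0, 6.1 and 6.6% of trials with complete baselines (rho 0.3, 0.5, 0.7). With 16 of 18 baselines per arm set aside it rejects in 9.4, 10.0 and 11.2%. The SAP names no small-sample method.

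**The case against.** The strongest reply is that an undosed baseline is plainly intended, and most of this stands. The first-dose rule is explicit. The sentence naming Visit 3 speaks of the end of treatment, which Visit 3 cannot be. Section 6.3 treats only Visits 4 and 8 as ends of treatment periods and plans ertugliflozin sampling only there. The SAP defines effects as change from baseline. The HFrEF/HFpEF stratum, "which will be assessed based on the 2D echo at the time of the baseline physiological testing", comes from a Visit 3 procedure: "The randomization visit procedures will include measures of natriuresis, renal and systemic hemodynamic function, neurohormonal assessments, echocardiography". Stratified allocation therefore has to wait for at least one Visit 3 measurement. Even so, the listing of Visit 3 stands in two operative places, one of them the hands-on preparation text.

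For Visits 4 and 8 it can be argued that the visit-specific text outranks the general instruction, and that protocol section 4.3 describes glycosuria as continuous over the dosing interval. The first is a reasonable guess, but the protocol states no such precedence. The second may limit the difference between timings, but it concerns glucose, not sodium or lithium. The laboratory manual may settle the timing; it was not available here, and the protocol would still contradict itself.

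A reader might infer that the primary estimate will be biased toward no effect. The documents do not support that. A site would have to override the first-dose rule, and an early FE(Li) effect, which no passage documents, would have to exist.

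**Conclusion.** The plan is wrong as written, with moderate severity. The contradiction at Visits 4 and 8 is certain from the text. Its consequence is an ambiguous estimand and possibly added variability, of a size the documents do not allow anyone to compute. A reader might take it as favouring one arm, but identical timing rules in two blinded arms give no ground for that.

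The Visit 3 listing is probably a slip. If it were followed, the loss would be about 15, 25 or 35% of the effect for f = 0.5 and rho of 0.3, 0.5 or 0.7, and smaller for smaller f. Those figures rest wholly on assumed f and rho and on equal variances at the two visits. What holds regardless is that the SAP 1.1 model depends on a condition it does not state and that the protocol, read literally, contradicts.

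**What to change.** 1. Reconcile the section 2 general instruction, the two section 2 visit-specific sentences and section 6.3 into one timing statement for each of Visits 3, 4 and 8. It should be identical across sites and in the laboratory manual. The choice of timing belongs to the sponsor and investigators.
2. Record on the eCRF the time of any study-drug intake relative to the measurements at those three visits.
3. State in SAP 1.1 that the model without a treatment main effect requires Visit 3 values obtained before any study drug. Identify any post-dose Visit 3 values before unblinding, in both arms, and add a sensitivity analysis excluding them. Use small-sample inference, for example Kenward-Roger, in place of a Wald z test; that adjustment was not itself simulated here.
4. Note in the SAP that patients whose Visit 3 value is excluded also lose their change scores in the regressions under 2.1–2.2 and 3.4–3.6.

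The cost is one protocol clarification, one eCRF field at three visits and a little more analysis work. No extra patients or procedures are needed. The sensitivity analysis also gives up some placebo baselines that carry no drug effect, because values are flagged while the arms are still blinded.

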3. STUDY POPULATION

Version number: 6.0 23-APR-2020

Population (base)

The study population will be selected from the outpatient clinics from hospitals based in the Netherlands (Groningen) and Canada (Toronto).

Inclusion criteria:

- 1. Male or female subjects diagnosed with T2D \geq 12 months prior to informed consent;
- 2. eGFR \geq 30 ml/min/1.73m²;
- 3. Age >18 years;
- 4. HbA1c 6.5%-10.5%;
- 5. Body Mass Index (BMI) 18.5-45.0 kg/m²;
- 6. Blood pressure $\leq 160/110$ and $\geq 90/60$ at screening,
- Heart failure with New York Heart Association (NYHA) class 2-3 symptoms and ejection fraction ≥20%
- 8. Stable dose of maximally tolerated ACE inhibitor, angiotensin receptor blocker or renin inhibitor for at least 30 days
- 9. Stable diuretic dose for at least 30 days at the time of baseline physiological assessment
- 10. BNP levels at baseline \geq 100 pg/ml (no atrial fibrillation), \geq 200 pg/ml if in atrial fibrillation

Exclusion criteria:

- 1. Type 1 Diabetes;
- 2. Leukocyte and/or nitrite positive urinalysis that is untreated;
- 3. Severe hypoglycaemia within 2 months prior to screening;
- 4. History of brittle diabetes or hypoglycaemia unawareness based on investigator judgement;
- 5. Unstable coronary artery disease with acute coronary syndrome, percutaneous intervention or bypass surgery within 3 months;
- 6. Clinically significant valvular disease;
- 7. Congestive heart failure secondary to an infiltrative cardiomyopathic process (for example amyloid) or pericardial constriction;
- 8. Uncontrolled systemic hypertension (systolic blood pressure >160 mmHg and/or diastolic blood pressure >110) or systemic hypotension (systolic blood pressure < 90/60 mmHg);
- 9. Bariatric surgery or other surgeries that induce chronic malabsorption;
- 10. Anti-obesity drugs or diet regimen and unstable body weight three months prior to screening;
- 11. Treatment with systemic corticosteroids;
- 12. Blood dyscrasias or any disorders causing hemolysis or unstable red blood cells;
- 13. Pre-menopausal women who are nursing, pregnant, or of child-bearing potential and not practicing an acceptable method of birth control;
- 14. Participation in another trial with an investigational drug within 30 days of informed consent;
- 15. Alcohol or drug abuse within three months prior to informed consent that would interfere with trial participation or any ongoing clinical condition that would jeopardize subject safety or study compliance based on investigator judgement;
- Liver disease, defined by serum levels of alanine transaminase, aspartate transaminase, or alkaline phosphatase >3 x upper limit of normal as determined during screening;
- 17. Active malignancy at the time of screening;
- 18. Allergy to iodine-based substances if receiving iohexol for GFR measures

Any disqualifying clinical or biochemical parameter may be repeated, at the discretion of the investigator and where there is a clinical reason to do so. The repeat value should be assessed prior to the subject recorded as having screen failed. If the repeat value falls within the ranges defined by the protocol and the patient meets all other inclusion criteria, the patient is eligible for the study.

